### **7.2.2.2. Congenital Anomaly**

Congenital anomaly reported in Phase III SPTL treatment studies, reported in ARIOS study (up to 1 year; after 1 year) will be summarized by treatment group. Congenital anomalies will be included in SAE listing.

### **7.2.2.3. Death**

A listing of infant deaths will be provided.

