consent and medical release when the woman's acute episode of preterm labor has resolved and prior to discharge from the hospital for the treatment of preterm labor. The infant will be allowed to be consented into the study until the later date of either the date of discharge from the birth hospitalization or up to 9 months corrected age (to allow for the infant's 9-month Child Health Inventory [CHI] and ASQ-3 data collection) via follow-up contact from the research coordinating center-principal investigator (RCC-PI) to the parent/legal guardian. This follow-up contact and informed consent discussion may occur via telephone with signed consent and medical releases transmitted via mail or courier. Infants and children will be followed at prespecified intervals until they reach 24 months chronological age (see [Table 2](#)). This study does not require medical interventions or study visits to an investigational site. Instead, parents or legal guardians will be prompted at certain time points to complete developmental questionnaires and other data on their children's health status via an electronic device. Data collected during this follow-up study will be managed by a centralized RCC. Regionally based pediatricians will serve as study principal investigators (referred to as RCC-PIs) for this study. All communications the RCC-PI has with the parent/legal guardian or the child's HCP will occur remotely; there will be no clinic visits. An overview of the study design is shown in [Figure 1](#).

Figure 1 **Study Design**

EDD = estimated date of delivery; HCP = health care provider; RCC = research coordinating center; RCC-PI = research coordinating center-principal investigator; SPTL = spontaneous preterm labor.

Electronic data capture (eDC) tools and processes including electronic case report forms (eCRF) and electronic patient-reported outcome devices will allow entry of data, regardless of when it is obtained. If at any time the data suggest any developmental delay, the RCC-PI will refer the child to a specialist (if not already under the care of a specialist) for formal evaluation and additional assessments. The child's local primary care pediatric

provider will be asked to provide routinely available data on the child to the RCC. Additional contacts may occur at the discretion of the RCC personnel to complete the data collection.

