### 2.2. Study Objective(s) and Endpoint(s)

Objectives	Endpoints

To characterize the clinical safety in terms of infant and child morbidity and mortality in infants and children exposed to retosiban or comparator in utero

	

Proportion of infants and children with newly diagnosed (after 28 days post EDD) chronic medical conditions by type of condition will be recorded and include the following:

Respiratory conditions

Chronic lung disease

Reactive airway disease

Vocal cord paralysis

Airway obstruction

Neurological conditions

Cerebral palsy

Seizure disorder

Hydrocephalus requiring shunt

Sensory conditions

Vision

Vision impairment

Blindness in 1 or both eyes, or sees light only

Hearing

Hearing impairment

Deafness in 1 or both ears

Hearing impaired, uncorrected even with aids

Gastrointestinal conditions

GERD (moderate to severe)

Tube/parenteral feeding

Short bowel syndrome

Cardiovascular conditions

Pulmonary hypertension

Hypertension

Renal conditions

Renal impairment requiring dialysis

Growth parameters

Poor weight gain

Reduced length

Reduced head circumference

Failure to thrive

Proportion of infants and children with newly diagnosed (after 28 days post EDD) congenital anomalies

Proportion of infant and child deaths that occur after 28 days post EDD and until 24 months chronological age

Objectives	Endpoints

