## 6.2. Disposition of Subjects

Analyses of disposition data will be based only on the Infant Safety population as defined in Section 4.

Subject status with respect to study status will be summarized in relation to:

- Enrolled
- Not enrolled
- Died in treatment studies
- Study completion and withdrawal/death

The number and percentage of subjects with the above study status will be reported by treatment group. Reasons for withdrawal will be presented.

Subject status with respect to each study milestone will be summarized in relation to:

- Treated at treatment studies
- Infant consented to ARIOS
- Infant not consented to ARIOS
- Enrolled at ARIOS

The number and percentage of subjects with the above study milestone will be reported by treatment group. The number and percentage of subjects reaching each study milestone after enrolling in ARIOS (infant death, 9 months, 18 months, and 24 months) will be presented.

A completed subject is defined as one who has completed all phases of the study up to and including the 2-year assessment. Note: due to protocol amendment 02 which updated the total study duration to 2 years, some infants may have data collected after the 2-year assessment.

Subject disposition data will also be listed. All disposition summaries will be performed using the Infant Safety population.

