### 7.2. Safety Analyses

All safety summaries will be performed for both populations as defined in Section 4. A listing of all safety data will be presented.

The primary objective of the planned analysis will be to use descriptive statistics to describe the safety and morbidity and mortality outcomes of children exposed to treatment during the Phase III SPTL studies investigating retosiban or comparator for the treatment of SPTL up to 24 months chronological age. The endpoints to be descriptively summarized are those described in Section 2.2. Descriptive statistics will be calculated by treatment group and/or time (up to 24 months chronological age), where appropriate.

For binary outcomes, all summary tables will include the number and percentage of subjects with the response/event. All summary tables will include N for each group (i.e., the total number of subjects in each treatment group).

The focus will be on collecting the safety outcomes as defined in the objectives (e.g., death) and serious AEs (SAEs), including congenital anomalies.

Nonserious AEs will not be tracked. All SAEs and safety outcomes will be followed until resolution, stabilization, or loss to follow-up.

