**10.8.4. ICH Listings**

ICH Listings					
No.	Population	IDSL / TST ID / Example Shell	Title	Programming Notes	Deliverable [Priority]
Subject Disposition					
37	ARIOS Safety		Study Disposition		
Demographics					
38	ARIOS Safety		Demographic and Baseline Characteristics		
43	ARIOS Safety		Race and Racial Combinations		
Adverse Events					
42	ARIOS Safety		Infant Serious Adverse Events		
44	ARIOS Safety		Infant Deaths		

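### The primary mortality proportion is promised as n and % in SAP 7.2 but is given only an ARIOS-only listing; the disposition counts of death lack the endpoint's start point and a stated denominator

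*SAP*

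**What the plan says.** Protocol Section 2 (Table 1) lists mortality under the primary objectives. SAP 2.2 repeats the endpoint: "Proportion of infant and child deaths that occur after 28 days post EDD and until 24 months chronological age".

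The general rules in SAP 7.2 are clear:

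- "The endpoints to be descriptively summarized are those described in Section 2.2".
- "For binary outcomes, all summary tables will include the number and percentage of subjects with the response/event".
- "All safety summaries will be performed for both populations as defined in Section 4".

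The specific provisions for death are narrower. SAP 7.2.2.3 reads in full: "A listing of infant deaths will be provided". In SAP Table 3 the row for death is marked for a listing only. The safety tables in SAP 10.8.3 include none for death. SAP 10.8.4 has Listing 44, "Infant Deaths", for ARIOS Safety.

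Deaths also appear in SAP 6.2. It plans n and % by treatment group for deaths in the treatment studies and for completion versus withdrawal or death. It also plans n and % of infants reaching milestones after ARIOS enrolment, infant death being one. On population it says: "Analyses of disposition data will be based only on the Infant Safety population as defined in Section 4".

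Two other provisions matter. Protocol 3.1 allows consent until "the later date of either the date of discharge from the birth hospitalization or up to 9 months corrected age". SAP 10.6.2 treats missing safety data as absence of the event.

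**The concern.** The general rule and the display list disagree for a primary endpoint, and the SAP does not explain why. Where it does cut an outcome to listings (exploratory health outcomes, SAP 7.2.6), it says so and gives low enrolment as the reason. SAP 2.1 refers to Section 8 for analyses that will not be performed, but Section 8 names none. The absence of a death table therefore looks like an omission rather than a decision.

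In a descriptive study the proportion is the result. If the only percentages for death come from disposition tables, the reader gets figures whose window opens at a different time from the endpoint's and whose denominator must be guessed. If the Infant Safety population is used with the missing-data rule, infants nobody followed are reported as alive.

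**Working it through.** The documents state no mortality figure, sample size or test for this endpoint, so there is nothing to reproduce. The check traces the endpoint through the displays and then sizes the denominator question.

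**1. Which displays carry each endpoint (SAP Table 3, 10.8.2 to 10.8.4)**

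| Endpoint group | Infant Safety table | ARIOS Safety table |
|---|---|---|
| SAEs | 10.5 | 20.5 |
| Chronic conditions | 10.6 | 20.6 |
| Neurodevelopment | 10.7, 10.8 | 20.7, 20.8 |
| Neurodevelopmental impairment | 10.9 | 20.9 |
| Congenital anomalies | 10.10 | 20.10 |
| Death | none | none (Listing 44 only) |

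Death is the only one of these without a pair of summary tables. A fatal event may be counted in Tables 10.5 and 20.5, but those are organised by system organ class and preferred term, not by fatal outcome.

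**2. The SAP 6.2 counts against the endpoint**

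- *Start.* The endpoint opens at 28 days post EDD; the milestone count opens at ARIOS enrolment. Deaths before 28 days post EDD belong to the treatment studies (Protocol 3.1). A death after that date but before enrolment is inside the endpoint window. SAP 6.2 has no explicit category for it, and Listing 44 excludes it. Yet SAP Section 4 places infants who died before enrolment in Infant Safety.
- *Length of the gap.* If the 9-month limit governs, the gap can last up to 9 − 28/30.44 = 9 − 0.92 = 8.1 months. It can be longer if birth-hospital discharge is later, and shorter with earlier consent.
- *End.* SAP Section 4 excludes data beyond the 2-year assessment from summaries, so the upper limit is largely handled.
- *Denominator.* SAP 6.2 fixes the population for disposition tables but does not say whether milestone percentages divide by enrolled infants or by all of Infant Safety.

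**3. Size of the two candidate denominators**

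Inputs: enrolled infants from the Amendment 02 justification in Protocol Appendix 1 (placebo 6, atosiban 43, retosiban 49; 6 + 43 + 49 = 98). Treatment-study group sizes are from Protocol 1.1.1: NEWBORN-1 placebo 13 and retosiban 10; ZINN atosiban 47 and retosiban 50. Retosiban is therefore 10 + 50 = 60, and the total is 13 + 47 + 60 = 120. **Assumption:** these sizes, quoted beside the time-to-delivery results, equal the Infant Safety groups.

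| Group | Enrolled | Infant Safety (assumed) | Never enrolled | Never enrolled, % | One death, enrolled | One death, Infant Safety |
|---|---|---|---|---|---|---|
| Placebo | 6 | 13 | 13 − 6 = 7 | 53.8 | 1/6 = 16.7% | 1/13 = 7.7% |
| Atosiban | 43 | 47 | 47 − 43 = 4 | 8.5 | 1/43 = 2.3% | 1/47 = 2.1% |
| Retosiban | 49 | 60 | 60 − 49 = 11 | 18.3 | 1/49 = 2.0% | 1/60 = 1.7% |
| Total | 98 | 120 | 22 | 18.3 | | |

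**4. Effect of the missing-data rule**

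On Infant Safety, SAP 10.6.2 would count the roughly 22 never-enrolled infants as survivors, apart from any recorded as dead. The share is uneven: about 7 of 13 on placebo against 11 of 60 on retosiban. How many of the 22 died before 28 days post EDD is not stated.

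**The case against.** The strongest reply is that mortality is already covered. SAP 7.2 commits to summarizing every Section 2.2 endpoint, SAP 6.2 plans n and % for infant death after enrolment, and Tables 10.1 and 10.2 match those plans. An infant must be alive at 28 days post EDD to be eligible (Protocol 4.2), so deaths after enrolment do fall inside the window. Deaths in the treatment studies have their own row. Listing 44 with the group sizes gives the crude proportion among enrolled infants. The study has no test, and the sponsor already regards the placebo group as too small for meaningful long-term comparison.

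Much of this stands, and it rules out several stronger readings that a reader might infer:

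- *That mortality has no planned estimate.* SAP 6.2 and 7.2 say otherwise.
- *That the disposition denominator is wrong.* It is unstated. A milestone reached after enrolment could well be a percentage of enrolled infants, and the table shells are in a separate document not available here.
- *That deaths before enrolment disappear from every output.* Listing 44 excludes them, but Infant Safety includes such infants, and no text says which disposition row they fall in. No such death is documented, and the protocol prefers consent before the mother leaves hospital.
- *That the denominator changes the picture in every arm.* It moves a single death noticeably only in placebo, because that group has 6 enrolled infants.

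The reply does not remove the inconsistency. The crude proportion from Listing 44 covers enrolled infants only, whereas SAP 7.2 promises both populations. That the study is descriptive does not help, because the descriptive proportion is itself the primary result.

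**Conclusion.** The point holds as a specification gap in a primary endpoint. SAP 7.2 promises n and % in both populations; SAP 7.2.2.3, Table 3 and Appendix 8 supply a listing for one. The counts in SAP 6.2 partly fill the gap, but they start at enrolment, state no denominator and assign no explicit category to deaths between 28 days post EDD and enrolment.

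The largest consequence is on Infant Safety, where about 22 of 120 infants (about 7 of 13 on placebo) would be treated as survivors unless recorded as dead. This rests on the assumption that the treatment-study group sizes equal Infant Safety. The single-death percentages (placebo 16.7% v 7.7%) are illustrative and matter little in the other arms. The documents do not support saying that mortality will go unreported. They support saying that no planned display reports it as SAP 2.2 defines it, and this should be corrected before unblinding, since SAP Section 8 rules out later changes.

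**What to change.** Add one death table by treatment group to SAP 7.2.2.3, Table 3 and Appendix 8, giving n and % of deaths after 28 days post EDD to 24 months chronological age:

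- **ARIOS Safety:** denominator is enrolled infants.
- **Infant Safety:** denominator is infants known to be alive at 28 days post EDD.
- **Unknown vital status:** its own row, not counted as survival, with the rule in SAP 10.6.2 disapplied for this table.
- **Separate rows:** earlier fetal and neonatal deaths; and, where known, deaths between 28 days post EDD and enrolment.

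Extend Listing 44 to Infant Safety. State the denominator of the milestone percentages in SAP 6.2 and say in which row a death before enrolment is counted.

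The cost is one table in two populations, one change of listing population and a few sentences of text. No new data collection is implied. The treatment studies' final assessment is at 28 days post EDD and ARIOS does not follow infants without consent, so later vital status may be largely unknown for the never-enrolled. The separate row makes that visible.

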## **7.2.3. Neurodevelopment Assessment at 9, 18, and 24 months**

Neurodevelopment will be assessed by determining the proportions of infants diagnosed with developmental delays listed below at 9, 18, and 24 months of age, corrected for prematurity.

Endpoints related to Ages and Stages Questionnaire version 3 (ASQ-3) score and developmental evaluation described in Section 2.2 will be descriptively summarized at 9, 18, and 24 months by treatment group. For subjects with an ASQ-3 score in the black zone ( $\geq 2$  standard deviation [SD] below the mean) for any domain and referred for development evaluation, number of infants and percentage with Bayley Scales of Infant Development 3rd edition (BSID-III) and non-BSID-III results will be summarized. For subjects with an ASQ-3 score in the black zone for any domain, referred for development evaluation, but no assessment done, reason of no assessment done will be summarized. In addition to endpoints described in Section 2.2, number of infants and percentage with moderate or severe developmental delay using non BSID-III score will be summarized.

For BSID-III score, scaled scores for cognitive, receptive communication, expressive communication, fine motor, and gross motor will be derived from the subtest total raw scores and range from 1–19, with a mean of 10 and an SD of 3. Language composite scores will be derived from sums of receptive communication and expressive communication scaled scores. The composite score will be scaled to a metric with a mean of 100 and an SD of 15, and range from 40–160.

Endpoints related to Modified Checklist for Autism in Toddlers Revised with Follow-Up (M-CHAT-R/F) described in Section 2.2 will be descriptively summarized at 18, and 24 months by treatment group.

Endpoints related to Child Behavior Checklist for Ages 1.5 to 5 (CBCL/1.5-5) and cerebral palsy in Section 2.2 will be descriptively summarized at 24 months by treatment group.

Neurodevelopment assessment data will be presented in listings.

## **7.2.4. Neurodevelopment Assessment at 3, 4, and 5 years**

New neurodevelopmental impairment from Question 8 in Modified Child Health Inventory (CHI) will be listed.

### **7.2.5. Neurodevelopment Impairment at the End of Study**

Number of infants and percentage of neurodevelopment impairment endpoints and individual components will be summarized at the end of study (24 months). Individual components at the end of study are listed in Section 2.2.

Motor composite score will be derived from fine motor and gross motor scaled scores in a similar fashion to language composite score described in Section 7.2.3

### **7.2.6. Health Outcome**

Due to the early termination of the intervention studies (NEW-BORN 1 and ZINN) and the subsequent low enrolment in this study, exploratory health outcome data will only be provided in listings.

## **8. DEVIATION OF PLANNED ANALYSES FROM PROTOCOL**

No changes will be made to the planned analyses after the breaking of the study blind.

## 10. APPENDICES

Section	Appendix
RAP Section 4 : Analysis Populations	
Section 10.1	Appendix 1 : Protocol Deviation Definitions
RAP Section 5 : General Considerations for Data Analyses & Data Handling Conventions	
Section 10.2	Appendix 2 : Time and Events
Section 10.3	Appendix 3 : Treatment States and Phases
Section 10.4	Appendix 4 : Data Display Standards & Handling Conventions 

• Study Treatment & Sub-group Display Descriptors

• Baseline Definitions & Derivations

• Reporting Process & Standards

Section 10.5	Appendix 5 : Derived and Transformed Data 

• General, Study Population & Safety

• Efficacy

Section 10.6	Appendix 6 : Premature Withdrawals & Handling of Missing Data 

• Premature Withdrawals

• Handling of Missing Data

Other RAP Appendices	
Section 10.7	Appendix 7 : Abbreviations & Trade Marks
Section 10.8	Appendix 8 : List of Data Displays

**10.1. Appendix 1: Protocol Deviation Definitions**

Subject compliance to the protocol will be evaluated prior to database freeze and unblinding the study and subjects with significant protocol deviations will be identified. Summary of protocol deviation will not be presented.

## 10.2. Appendix 2: Time and Events

Event	28 Days Post EDD	Months						
		2	6	9	12	15	18	21
Written informed consent 		←	→					
Baseline characteristics and demographic data	X 							
RCC confirms and updates contact information from the parent/legal guardian	X							
Parent/legal guardian completes CHI 		X	X	X	X	X	X	X
RCC-PI follows up with HCP and reviews medical or other records to confirm parent-reported outcomes								→
RCC-PI reviews CHI results and refers to birth-defect evaluator based on results								→
Parent/legal guardian completes productivity questionnaire 								
Parent/legal guardian completes ASQ-3 				X 			X 	X  →
RCC-PI reviews ASQ-3 results and refers for developmental evaluation based on results 								→
Parent/legal guardian completes M-CHAT-R/F 							X	X
Parent/legal guardian completes CBCL/1.5–5 								X
RCC-PI refers child to specialist for cerebral palsy assessment (if required) 								X

ASQ-3 = Ages and Stages Questionnaire-3; CBCL/1.5–5 = Child Behavior Checklist for ages 1.5 to 5; CHI = Child Health Inventory; EDD = estimated date of delivery; HCP = health care provider; M-CHAT-R/F = Modified Checklist for Autism in Toddlers-Revised with Follow-Up; RCC = research coordinating center; RCC-PI = research coordinating center-principal investigator.

Note: All specified completion windows for applicable questionnaires (CHI, ASQ-3, CBCL/1.5–5, M-CHAT-R/F, and productivity) are provided to help standardize the data and avoid overlap. Information captured outside of these windows will be collected and analyzed separately, and questionnaires completed outside the completion window will not be considered protocol deviations.

1. Collected at the start of the Phase III spontaneous preterm labor (SPTL) treatment studies until the later date of either the date of discharge from the birth hospitalization or up to 9 months corrected age (to allow for the infant's 9-month CHI and ASQ-3 data collection).
2. Captured in Phase III SPTL treatment studies and combined with child follow-up data for analyses.
3. A positive response by the parent/legal guardian may trigger follow-up with the relevant HCP and/or medical record review for confirmation or more details on the condition or hospitalization. At each time point, the completion window of the CHI is +6 weeks.
4. Completed if infant has been treated by a specialist or has had an emergency room/urgent care or hospital visit. The completion window for the productivity questionnaire is +2 weeks from the date of completion of the relevant CHI.
5. Based on infant's corrected age. The completion window for the ASQ-3 is +30 days at Month 9 and  $\pm$ 30 days at Months 18 and 24.
6. If the parent/legal guardian receives a referral, then a qualified specialist will complete required assessments.
7. The CBCL/1.5–5 and M-CHAT-R/F questionnaires will be completed for all infants. The completion window for the CBCL/1.5–5 and M-CHAT-R/F is +6 weeks at 18 months (M-CHAT-R/F only) and +12 weeks at 24 months.
8. Referral will be made for infants who score in the black zone for the gross motor skills domain on the 24-month corrected age ASQ-3 and do not have an existing diagnosis of cerebral palsy.

**10.3. Appendix 3: Treatment States and Phases**

Not applicable.

This is a safety follow-up study of infants and children exposed to treatment during their mother's participation in a Phase III SPTL treatment study of retosiban or comparator for SPTL. Infants and children enrolled in this study will not be administered any investigational product.

